Table 1 presents demographic and baseline characteristics for subjects with r/r AML enrolled and treated in Phase 2 Dose Expansion. The median age of subjects was 60 years, 60% of subjects were male, and 81% were White. The 10-day group was nearly equally divided between the sexes (51% men) compared with the 5-day group (70% men), but all other demographic characteristics were similar across treatment groups. Most subjects (73%) had an ECOG status of 1 at baseline and had received a median of 2 prior regimens with up to 10 prior regimens including 11% with

prior HMA treatment. The median time since diagnosis was 261 days (range 8 to 3214 days). Of note are the poor prognostic features of subjects treated in this study (18% of subjects had prior HCT and 41% had poor risk cytogenetics).

	5-Dav					10-Dav					
Characteristic		60 mg/m ² (N=24)		90 mg/m ² (N=26)		Total (N=50)		$\frac{60 \text{ mg/m}^2}{(\text{N}=53)}$		- Total (N=103)	
Age, yr	Median Range	58.4 22.0	3 -77.0	65.50 30.0-81.7		62.34 22.0-81.7		57.47 29.2-82.5		60.13 22.0-82.5	
Gender (n, %)	Male Female	15 9	(63) (38)	20 6	(77) (23)	35 15	(70) (30)	27 26	(51) (49)	62 41	(60) (40)
ECOG (n, %)	0 1 2	2 20 2	(8) (83) (8)	3 20 3	(12) (77) (12)	5 40 5	(10) (80) (10)	9 35 9	(17) (66) (17)	14 75 14	(14) (73) (14)
Time Since Diagnosis to C1D1 (Days)	Median Range	369.5 27-3198		292.0 8-1611		342.0 8-319	98	177.0 17-3) 3214	261.0 8-321	14
BM Blasts (%)	Median Range	34.0 9-9	3	35.5 2-9	; 94	35.0 2-9	94	32.0 4-9) 95	33.0 2-9	5
PB Blasts (%)	Median Range	5.0 0-95		14.0 0-8) 81	10.0 0-9	95	2.5 0-9	; 99	6.0 0-9	9
WBC (x10 ⁹ /L)	Median 1.65 Range 0.3-18		5 -18.7	2.1 0.3	2 -18.6	1.7 0.3	0 -18.7	2.1 0.2	0 2-75.5	1.8 0.2	0 -75.5
Cytogenetics (n, %) (Company Assessment)	n Better Risk Int Risk Poor Risk Not evaluable	24 0 12 9 3	(50) (38) (13)	26 0 14 11 1	(54) (42) (4)	50 0 26 20 4	(52) (40) (8)	53 0 26 22 5	(49) (42) (9)	103 0 52 42 9	(50) (41) (9)
Prior Decitabine or Azacitidine (n, %)		1	(4)	2	(8)	3	(6)	8	(15)	11	(11)
Prior HCT (n, %)		5	(21)	5	(19)	10	(20)	9	(17)	19	(18)
Number of Prior Regimens	Median Range	2.5 1-5		2.0 1-10		2.0 1-1	0	2.0 1-7) 7	2.0 1-1	0
Time Since Last Anti-Leukemia Therapy (n, %)	n <6 Months ≥6 Months Unknown	24 19 5 0	(79) (21)	26 20 5 1	(77) (19) (4)	50 39 10 1	(78) (20) (2)	53 43 10 0	(81) (19)	103 82 20 1	(80) (19) (<1)

Table 1:Summary of Demographic and Baseline Characteristics:
Relapsed/Refractory AML Subjects (Phase 2, Study SGI-110-01)

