11.6.3 Subgroup and Exploratory Analyses

Subgroup analyses will be performed to explore how OS is influenced by baseline variables and the individual TC therapy administered, and to evaluate the treatment effect at different levels of each of these variables. The Kaplan-Meier analysis and Cox model will be performed by subgroup levels of the baseline variables and each TC therapy listed below:

- Age ($<75, \geq 75$).
- Baseline cytogenetic risk (poor-risk, others; see Appendix 3).
- ECOG performance status (0-1, 2).
- Number of prior regimens ($\leq 2, >2$).
- Prior HCT (yes, no).
- Baseline BM blasts ($\leq 40\%$, >40%).

- Baseline total WBC counts ($\leq 20,000/\mu$ L, $> 20,000/\mu$ L).
- Study center region (North America, Europe, Asia-Pacific, Other).
- Race (White, Black, Asian, Other).
- Presence of baseline specific gene mutations or gene expressions for each gene (yes, no).
- Individual preselected TC (high intensity, low intensity, BSC).
- Additional subgroups may also be further described in the Statistical Analysis Plan.

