7.3.4 Subgroup Analysis

Subgroup analyses will be performed to explore how the treatment effect on OS is influenced by baseline variables, extent of treatment received, and the individual TC therapy administered. To evaluate the treatment effect at different levels of each of these variables, the Kaplan-Meier analysis and Cox model will be performed separately by each level of each variable as follows:

- Age ($<65, \geq 65$).
- Age ($<75, \geq 75$).
- Sex (Male, Female).
- Baseline cytogenetic risk (poor-risk, others).
- Baseline ECOG performance status (0-1, 2).
- Response to initial intensive induction therapy (refractory, first relapse, >1 relapse).
- Prior HCT (yes, no).
- Baseline BM blasts ($\leq 40\%$, >40%).

- Baseline PB blasts ($\leq 30\%$, >30%).
- Baseline total WBC counts ($\leq 20,000/\mu$ L, $> 20,000/\mu$ L).
- Study center region (North America, ROW).
- Race (White, Black, Asian, Other).
- Presence of baseline genetic mutations or gene expressions for each gene such as FLT3-ITD, NPM1, CEBPA biallelic, TP53, ASXL-1, and RUNX-1 (yes, no).
- Treatment cycles received (<4 cycles vs \geq 4 cycles).
- Treatment cycles received (<6 cycles vs \geq 6 cycles).
- Individual preselected TC (high intensity, low intensity, BSC).

The treatment effect (HR and 95% CI) for each of these subgroups will be displayed on Forest plots.

Subjects with missing a value for a variable used to define a subgroup will be excluded from that subgroup analysis except for subgroups with an "Other" category. In those subgroups, subjects with missing values will be included in the Other category.

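### SAP 7.3.4 moves missing subgroup values into an Other level, on a natural reading including unknown karyotype, and compares levels only through separate hazard ratios

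*SAP*

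**What the plan says.** SAP 7.3.4 sets out subgroup analyses of OS. Their stated purpose is to explore how the treatment effect is influenced by baseline variables, by the extent of treatment and by the TC therapy. The method is that "the Kaplan-Meier analysis and Cox model will be performed separately by each level of each variable as follows". Row HRs with 95% CIs go on forest plots. The section contains no treatment-by-variable term and no estimate of the difference between levels. Protocol 11.6.3 has none either. The only interaction term in the SAP is treatment-by-time in the EQ-5D model (7.3.2.10).

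For missing values the default is to leave the subject out of the subgroup concerned. Any subgroup that has an Other level is the exception: "In those subgroups, subjects with missing values will be included in the Other category".

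Two list entries have a residual level: "Race (White, Black, Asian, Other" and "Baseline cytogenetic risk (poor-risk, others". Neither has a row for unknown values. Randomization used a two-level cytogenetic factor, poor risk against other (Protocol 6.1), with cytogenetics assessed before randomization (Protocol 9.5.2). SAP 7.3.4 does not say whether the subgroup uses that stratum or the karyotype recorded on the CRF.

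**The concern.** There are two separate points.

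First, a missing value is not a category. Under the rule an unrecorded race is analysed as a race. If the rule reaches cytogenetics, an unknown karyotype is analysed as not poor-risk. Some of those subjects would in truth be poor-risk, which pulls the two cytogenetic rows towards each other. Cytogenetic risk is a stratification factor, and the SAP itself describes it as prognostic (3.1), so readers will look at this contrast.

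Second, asking how a variable influences the treatment effect is a question about the difference between levels. Separate models give an HR and CI within each level and leave the reader to compare them by eye. One row's CI excluding 1 while the other's does not is easily read as effect modification, although it often happens when the effect is the same in both rows. Enrollment stopped on a futility recommendation, and in that setting such patterns attract attention.

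**Working it through.** **The plan's own figure.** The documents give no subgroup power, so the check starts from SAP 4.0. With deaths = 4(1.960 + 1.282)² / (ln HR)², HR 0.692, 2-sided 0.05 and 90% power, the result is 311 deaths by Schoenfeld and 318 by Freedman, against the stated 315. Power at 277 deaths is 86.5%, against the stated 86%. Both reproduce, so the same approximation (variance of a log HR = 4/deaths under 1:1 allocation) is used below.

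**Dilution of the non-poor-risk row.** Inputs are the Phase 2 r/r AML cohort in Protocol Table 1: 0 better-risk, 52 intermediate, 42 poor and 9 not evaluable, of 103 (the text gives "41% had poor risk cytogenetics").
- Pooled row: 52 + 9 = 61. Unknown share: 9/61 = 14.8%.
- Unknowns among about 300 randomized: 300 × 9/103 ≈ 26.
- Poor-risk share of evaluable karyotypes: 42/94 = 44.7%. Applied to the unknowns: 0.447 × 9 ≈ 4.0, or 4.0/61 = 6.6% of the row.
- Assume true HRs of 0.692 (not poor-risk) and 1.0 (poor-risk), and mix log HRs as an approximation. Row HR = exp[(1 − 0.066) × ln 0.692] = 0.709. If every unknown is poor-risk, exp[(1 − 0.148) × ln 0.692] = 0.731.
- Varying the unknown rate from 2% to 15%, and the poor-risk fraction of unknowns from none to all, gives row HRs from 0.692 to 0.757.
- The shift to 0.709 is 0.066 × 0.368 = 0.024 on the log scale. The row's SE is √(4/(0.59 × deaths)), which is 0.18 at 220 deaths and 0.16 at 277. The shift is about one-seventh of an SE.

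**Chance differences between the two cytogenetic rows.** The final death count is not given. I take 220 to 277, where 277 is the SAP's fallback count and 220 is an assumed lower value, and split deaths 41:59 after the Phase 2 poor-risk share. For a common HR h, a row with d deaths has z = √(d/4) × |ln h|, and its CI excludes 1 with probability p = Φ(z − 1.96) + Φ(−z − 1.96). The chance that exactly one row excludes 1 is p₁(1 − p₂) + p₂(1 − p₁).

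| Common HR (no interaction) | 220 deaths | 277 deaths |
|---|---|---|
| 1.0 | 9.5% | 9.5% |
| 0.80 | 34.0% | 38.7% |
| 0.692 | 50.9% | 50.0% |

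An even split changes the 0.80 line only to 33.8% and 38.4%.

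**What an interaction estimate would deliver.** SE of the difference in log HRs = √(4/d₁ + 4/d₂).
- 220 deaths: √(4/90.2 + 4/129.8) = 0.274.
- 277 deaths: √(4/113.6 + 4/163.4) = 0.244.
- With no true interaction, the ratio of the two row HRs lies within 0.58 to 1.71 (220 deaths) or 0.62 to 1.61 (277 deaths) in 95% of trials.
- Power for a true ratio of 0.692 is Φ(0.368/SE − 1.96): 26.8% and 32.5%, or 27.5% and 33.4% with an even split.
- Nominal false-positive rate is 5% per variable, whatever the common HR. Over the 14 baseline list entries, the chance of at least one is 1 − 0.95¹⁴ = 51%. Counting the six named genes singly gives 19 entries and 1 − 0.95¹⁹ = 62%. Both treat the variables as independent, which they are not.

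**The case against.** The strongest reply on karyotype is that the SAP never names cytogenetics in the rule. Only race has a level labelled exactly Other; the cytogenetic level is called others. If the row uses the randomization stratum, every randomized subject should have a value and the rule would never apply. This stands as far as it goes: the text is ambiguous. But the rule speaks of subgroups in the plural, and cytogenetics is the only other entry with such a level. The documents also do not say how a not-evaluable karyotype was entered at randomization.

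A reader might go further and infer that the cytogenetic comparison is contaminated. The documents do not support that. Karyotype is a baseline variable, so the comparison within each row stays randomized. What changes is the mix of subjects in one row, and the effect is small at the only rate available, which comes from another study.

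On the second point, the analyses are called exploratory, sit outside the testing sequence in SAP 7.3.3, carry no decision rule and show CIs. That is correct, and it is why the issue is minor. A reader might infer that the forest plot will present chance differences as real ones. It can invite that reading, but the SAP makes no such claim. Nor do interaction p-values cure multiplicity: the 51% to 62% above shows that some variable will often look notable by chance. The gain is narrower. The estimate answers the question asked, and its error per variable is 5%, where contrasting the two rows' CIs misleads in 10% to 51% of trials.

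A reader might also see selective reporting in the SAP's omission of the protocol factor "Number of prior regimens" and its reduction of four regions to two. The SAP gives no reason, but it states that it supersedes the protocol's analysis plan (1.0). Its new induction-response subgroup is partly defined by prior regimens (7.2), and the two regions match the stratification factor. I do not ask for either to be restored.

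**Conclusion.** The point holds as a minor one, and it does not touch the primary analysis.

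The missing-value rule is explicit for race and probable for cytogenetics. For cytogenetics its effect is mild dilution: about 15% unknowns in the row and a row HR of about 0.71 in place of 0.692. This rests on the Phase 2 not-evaluable rate, a poor-risk HR of 1.0 and use of the CRF karyotype. With the stratum as source there may be no missing values. No figure is available for missing race.

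The lack of an estimated difference between levels is certain from the text. Its size rests on the assumed 220 to 277 deaths and the 41:59 split. An interaction estimate would guard against over-reading a difference. With power of about 27% to 33% for a ratio of 0.692, it could not rule out effect modification.

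**What to change.** In SAP 7.3.4:

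1. Replace the Other rule. Missing or not-evaluable values are excluded from the cytogenetic and race subgroups as from all others, or shown as their own row, with counts either way.
2. State whether the cytogenetic subgroup uses the randomization stratum or the CRF karyotype and, if the stratum, how a not-evaluable karyotype was entered.
3. For each baseline variable, fit one Cox model with treatment, the variable and their interaction. Show the ratio of HRs with its 95% CI beside the row HRs. Label it exploratory, unadjusted for multiplicity and low-powered. The entries based on cycles received are post-baseline and raise a different problem, which this change does not address.

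The cost is a paragraph of SAP text and a small programming change. If exclusion is chosen, a few subjects leave one row in each of two subgroups.

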7.3.5 Dealing with Technical Issues Caused by Small Cell Count

If technical issues (such as non-convergence or unstable variance) arise due to small cell counts caused by too many levels of stratification variables, the stratification variables will be collapsed in the following order, until the technical issues have been resolved:

- 1) Collapse pre-selected TC options (combine 2 or more of the TC comparators: high intensity, low intensity and BSC).
- 2) Collapse study center regions (combine North America and ROW) and collapse pre-selected TC options.

7.4 Safety Variables and Analyses

Unless otherwise specified, all safety analyses will be performed using the Safety Analysis Set which includes data from all subjects who receive any amount of study treatment (guadecitabine or TC; see Section 5.2). For all safety analyses, summaries by treatment group (guadecitabine and TC) will be provided. Additional displays of study treatment exposure and adverse events may be generated for each preselected TC option. Data will be summarized by guadecitabine and each TC option within a given preselected TC option.

Safety is assessed by subject-reported and investigator-observed AEs, and 30-day and 60 day allcause mortality, along with concomitant medications, physical examination, clinical laboratory tests (hematology, serum chemistry, and urinalysis), vital signs, ECOG performance status, and ECGs. Safety is also assessed by exposure to guadecitabine or TC, reasons for discontinuation, deaths and causes of deaths.

All safety data collected during the study will be included in the study database. All safety data collected during the study will be used for generation of safety summary tables, with the exception of AEs and medications. The AE and medication summary tables will only include treatment-emergent AEs and concomitant medications as defined in Sections 7.4.2 and 7.4.4.

7.4.1 Study Treatment Exposure

Cycle 1 Day 1 is defined as the first day of study treatment after randomization; cycle days are counted sequentially thereafter. Cycle 2 Day 1 is the first day of Cycle 2 regardless of treatment delays. The designated cycle duration is 28 days, but any cycle could be prolonged to >28 days to allow blood count recovery if deemed clinically necessary. This convention for determining the start and stop dates for cycles is maintained until treatment is permanently discontinued. For easy presentation, Cycle x Day y is often abbreviated as CxDy in this document and statistical outputs.

Frequency counts and percentages of dose cycles received (or CxD1 visits completed for subjects randomized to BSC), dose cycles delayed, and dose reduced cycles will be summarized by treatment group and will be based on dose administrations, dose reductions, and dose delays identified by the study site and collected on the study drug administration CRFs. Delayed cycles will be identified and reported by the study site. For LDAC, MEC, and FLAG, dose-reduced cycles will be identified and reported by the study site while for the guadecitabine, azacitidine, decitabine, and HiDAC treatment groups, a dose-reduced cycle will be defined as a cycle in which:

- the planned dose for cycles ≥ 2 is less than planned dose for Cycle 1, OR
- the actual total dose (mg) for any day in the cycle is ≥25% reduction from planned dose (mg) calculated from BSA and planned dose (mg/m²), OR
- the number of days of dosing in cycle is less than expected.

Summaries of delayed cycles and dose reduced cycles will be provided at both subject and cycle levels.

Dose intensity, presented as the incidence of subjects receiving <80% of their intended dose, will be summarized by cycle for the guadecitabine treatment group. Dose intensity will be calculated as the actual total dose divided by planned total dose for each treatment cycle.

Both completed or partially completed dose cycles are counted in these summaries. For BSC, cumulative dose, delayed cycles, dose-reduced cycles, and dose intensity will not be summarized.

7.4.2 Adverse Events

AE terms reported by study subjects or observed by investigators will be mapped to the appropriate System Organ Class (SOC) and Preferred Term (PT) according to the Medical Dictionary for Regulatory Activities (MedDRA). Severity of AE will be graded using Common Terminology Criteria for Adverse Events (CTCAE) version 4.03.

Treatment-emergent AEs are defined as events that first occurred or worsened after the first dose of study drug given on C1D1 (or the C1D1 visit date for subjects randomized to BSC) until 30 days after the last dose of study treatment (or until the Safety Follow-up visit date for subjects randomized to BSC), or the start of an alternative anti-leukemia treatment, whichever occurs first, with the following exceptions: events that occurred after 30 days beyond the last dose of study treatment (or after the Safety Follow-up visit date for subjects randomized to BSC), or the start of an alternative anti-leukemia treatment, whichever occurs first, with the following exceptions: events that occurred after 30 days beyond the last dose of study treatment (or after the Safety Follow-up visit date for subjects randomized to BSC), or the start of an alternative anti-leukemia treatment will also be considered treatment-emergent if the events are both serious and related to the study treatment. For the purpose of determining whether an AE is a treatment-emergent AE, incomplete AE start dates will be imputed conservatively.

All AE data collected in the study database will be listed, including those that are not treatment emergent. However, safety tables will be generated based only on treatment-emergent AEs.

An overall safety summary table containing counts and percentages of subjects with any AE, any AE Grade \geq 3, AE resulting in permanent treatment discontinuation, AE resulting in drug interruption, AE resulting in dose reduction, any serious AE (SAE), and subcategories of SAEs (fatal and non-fatal) will be produced by treatment group. A similar table with related AE counts will also be produced by treatment group. Related events are those that the investigator considered to be suspected to be related to study treatment as described in the study protocol.

The number and percentage of subjects experiencing AEs will be summarized by MedDRA SOCs (sorted alphabetically) with PTs sorted by decreasing frequency within each SOC. The number and percentage of subjects experiencing AEs will also be summarized by PT and sorted by event frequency. Related AEs, AEs Grade \geq 3, related AEs Grade \geq 3, serious AEs, related serious AEs, AEs with an outcome of death, AEs resulting in permanent treatment discontinuation, AEs resulting in drug interruption, and AEs resulting in dose reduction will be summarized similarly. In addition, AEs, related AEs, and SAEs will be summarized by SOC, PT, and CTCAE grade where subjects with multiple occurrences of the same AE will be counted once with its worst CTCAE grade.

7.4.3 **30- and 60-Day All-cause Mortality**

The 30- and 60-day all-cause mortality will be calculated as the proportions of subjects who have died within 30 or 60 days of study treatment initiation based on each subject's date of death relative to C1D1 (ie, date of death minus date of C1D1). Subjects who die within 30 days will also be included in the 60-day mortality calculations. To avoid using a different denominator for calculation of the percentage of 30- and 60-day mortality, subjects who were lost-to-follow-up

within 30- or 60-days from C1D1 (assumed to be a very small number, if any) will be considered alive for the corresponding 30- and 60-day mortality calculations.

In addition, a summary of all deaths, by cause of death (AE, progressive disease, other) and treatment group will be provided for the Efficacy Analysis Set (all randomized subjects)

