The TC comparator arm options and doses are described in greater detail in Section 7.2 and treatment duration will be based on approved prescribing information and institutional standard practice. Guadecitabine will be given SC at a dose of 60 mg/m² in 28-day cycles. For the first cycle guadecitabine will be given for 10 days on Days 1-5 and Days 8-12 or on Days 1-10. The second cycle will be either the 5-day regimen (Days 1-5) or 10-day regimen (Days 1-5 and 8-12 or Days 1-10) based on assessment of disease response and hematological recovery at the end of Cycle 1. In subsequent cycles guadecitabine treatment will be for 5 days only (Days 1-5). Guadecitabine treatment should be given for at least 6 total cycles in the absence of unacceptable toxicity or disease progression requiring alternative therapy. Beyond 6 cycles, treatment should continue as long as the subject continues to benefit based on investigator judgment.

Treatment cycles are intended to be repeated every 28 days. However, treatment delays are permitted to allow normal count hematological recovery in the absence of PB blasts, particularly with more intensive treatment such as guadecitabine 10-day regimen, HiDAC, MEC, and FLAG/Ida. Visits will occur on treatment days, as necessary. In addition, during the first 3 cycles, visits will occur weekly on Days 8, 15, and 22, then on Day 15 in Cycles 4-6. In Cycles >6, visits will only occur on treatment days (if necessary), with study specified assessments on Day 1. Additional visits based on treatment effect and blood counts may be done at the investigator's discretion. Subjects will attend a safety follow-up visit after the last study treatment. For subjects who discontinue study treatment before Cycle 6, long term follow-up visits will occur monthly until 6 months after the start of study treatment and then every 3 months thereafter. For subjects who discontinue study treatment after Cycle 6, long-term follow-up will be every 3 months.

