4.2 Discussion of Study Design

This trial compares the efficacy and safety of guadecitabine to TC in subjects with AML previously treated with induction therapy (even if that induction was not given as first-line therapy) using a
standard intensive chemotherapy regimen or a similar cytarabine+anthracycline based induction, who are refractory to induction or who have relapsed.

Standard intensive induction chemotherapy comprises 7 days of Ara-C and 3 days of an anthracycline (daunorubicin or idarubicin), known as the 7+3 regimen, which produces remission in 70%-80% of patients for whom the treatment is appropriate (Tefferi and Letendre 2012). Less intensive regimens due to patients' age and/or comorbidities are acceptable as long as they include cytarabine and an anthracycline, including the recently approved CPX-351. For patients with relapsed or refractory AML, treatment typically includes diverse regimens of high, medium, and low intensity. Cytarabine is included in many of these regimens, either as a single agent or in combination regimens. HMAs are also used, as discussed in Section 1.2.

TC, the control therapy for this study, includes the treatments listed in Section 4.1. These therapies have not been compared directly, and regional treatment standards vary. Hence, all of these are allowed. TC doses and schedules specified in Section 7.2 are based on prior published reviews and studies (Döhner et al 2015; Roboz et al 2014).

Eligibility criteria for this Phase 3 trial are similar to the eligibility criteria in the preceding Phase 1-2 study. This Phase 3 study additionally requires subjects to have BM or PB blasts \geq 5% at randomization.

The randomization ratio of 1:1 maximizes study power for the number of subjects and there is no ethical reason to deviate from the most efficient study design.

OS, the primary endpoint, is accepted as a gold standard endpoint to demonstrate clinical benefit of cancer therapies. Secondary endpoints complement the primary endpoint. Transfusion independence, CR and CRh, days out of hospital, HCT, and quality of life are clinically relevant measures of treatment benefit in this population. Safety will be assessed by comparing incidences of AEs across treatment groups according to the Common Terminology Criteria for Adverse Events (CTCAE) and by 30- and 60-day all-cause mortality.

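### Treatment-emergent AEs are compared between arms only as crude percentages, although time at risk may differ between guadecitabine and TC

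*SAP*

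**What the plan says.** Protocol 4.2 makes the AE comparison part of the safety assessment: "Safety will be assessed by comparing incidences of AEs across treatment groups". The same sentence adds 30- and 60-day all-cause mortality. SAP 7.4 sets the contrast as guadecitabine against pooled TC: "For all safety analyses, summaries by treatment group (guadecitabine and TC) will be provided". Displays by preselected TC option are optional.

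SAP 7.4.2 gives the measure, "The number and percentage of subjects experiencing AEs will be summarized by MedDRA SOCs", and limits it to the treatment-emergent window: "However, safety tables will be generated based only on treatment-emergent AEs". The window opens at the first dose (for BSC, the C1D1 visit) and runs "until 30 days after the last dose of study treatment (or until the Safety Follow-up visit date for subjects randomized to BSC"), or to the start of alternative anti-leukemia therapy if that comes first. Later events still count if they are both serious and related.

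Planned duration differs by arm. Protocol 4.1 states: "Guadecitabine treatment should be given for at least 6 total cycles in the absence of unacceptable toxicity or disease progression requiring alternative therapy". After that, guadecitabine continues while the investigator sees benefit. TC duration follows local labels and institutional practice (Protocol 4.1 and 7.2), and BSC subjects count as on treatment until progression (Protocol 5.4.1).

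**The concern.** A percentage of subjects with an event rises with the length of time each subject is observed. If the treatment-emergent window is longer in one arm, the percentage mixes the rate of events with time on treatment. A drug given for longer can then look more toxic at the same underlying rate.

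Neither document plans an AE measure that separates the two. SAP 7.4.1 summarizes cycles received, but does not link them to the AE tables. SAP 7.4.3 defines 30- and 60-day mortality over a fixed period, but for deaths only. What is at stake is the benefit-risk reading of events such as febrile neutropenia, pneumonia and sepsis. The AE comparison is descriptive, so no alpha or power is affected.

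**Working it through.** **Plan's own figures.** The documents give no AE rate or window length to reproduce. The survival assumptions used below are those of the sample-size section (SAP 4.0): median OS 4.5 months (TC) and 6.5 months (guadecitabine). They are consistent with the stated 315 deaths: at HR 0.692, two-sided 0.05 and 90% power, Schoenfeld's formula gives 311 and Freedman's 318. Power at 277 deaths is 86.5%, against the stated 86%.

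**Window length.** For k cycles of 28 days (SAP 7.4.1), ending with a 5-day course plus 30 days:

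w = 28(k − 1) + 4 + 30 days

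This gives 34 days for 1 cycle, 62 for 2, 90 for 3, 118 for 4 and 174 for 6. At 30.44 days per month, 62 days is 2.037 months and 174 days is 5.717 months.

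**Crude percentage at a common rate.** Take a constant first-event rate λ, the same in both arms, and a constant death hazard μ = ln 2 / median OS that ends the window early:

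P = λ/(λ + μ) × [1 − exp(−(λ + μ)w)]

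The rate λ and the TC cycles received are assumptions. At λ = 0.2 per month:

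- TC, 2 cycles: μ = 0.693/4.5 = 0.154. P = (0.2/0.354) × [1 − exp(−0.354 × 2.037)] = 0.565 × 0.514 = 29.0%.
- Guadecitabine, 6 cycles: μ = 0.693/6.5 = 0.107. P = (0.2/0.307) × [1 − exp(−0.307 × 5.717)] = 0.652 × 0.827 = 53.9%.

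With guadecitabine held at 6 cycles:

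| TC cycles | TC % (median OS 4.5) | Guadecitabine % (median OS 6.5) | Gap, points | Gap if median OS is 5.4 in both arms |
|---|---|---|---|---|
| 1 | 18.5 | 53.9 | 35 | 33 |
| 2 | 29.0 | 53.9 | 25 | 22 |
| 3 | 36.7 | 53.9 | 17 | 14 |
| 4 | 42.2 | 53.9 | 12 | 8 |
| 6 | 49.0 | 53.9 | 5 | 0 |

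A simulation of 1,000,000 subjects per arm agrees with these percentages to within about 0.2 points. In every scenario it returned equal events per person-month in the two arms (for example 0.200 and 0.200).

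**Other rates.** With 2 TC cycles and the planned OS medians, rates of 0.05, 0.1 and 0.4 per month give 8% vs 19%, 16% vs 34% and 49% vs 75% (TC first).

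**Earlier stopping.** The table closes windows only at death or at the end of the planned cycles. If windows instead end at random with mean m months, P = λ/(λ + 1/m). At λ = 0.2, means of 2 (TC) and 4 (guadecitabine) months give 0.2/0.7 = 28.6% and 0.2/0.45 = 44.4%, a gap of 16 points. Means of 2 and 3 months give 28.6% and 37.5%, a gap of 9. Equal means give no gap.

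**A single rate can mislead in the other direction.** Suppose 30% in each arm have the event in month 1 (on average at 0.5 month) and none later, with windows of 5 and 2 months. Then:

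- Guadecitabine: 0.30/(0.30 × 0.5 + 0.70 × 5) = 0.30/3.65 = 0.08 per month.
- TC: 0.30/(0.30 × 0.5 + 0.70 × 2) = 0.30/1.55 = 0.19 per month.

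Equal risk then looks more than twofold different, so an unsplit exposure-adjusted rate is not a sufficient repair.

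**The case against.** The strongest reply is that unequal exposure is not established. The window rule is the same for every active treatment, and no number of TC courses is fixed. Protocol 7.2 allows consolidation cycles of the same regimen, and Protocol Table 7 schedules the high-intensity regimens in Cycle 4 and later. A reader might infer that high-intensity TC is a fixed short course and that time at risk therefore differs by design. The documents do not support that; they support only that it may differ. The guadecitabine window is not unlimited either, since progression, toxicity, alternative therapy and death all close it.

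Second, the constant rate is doubtful. The 10-day regimen is confined to Cycles 1 and 2 (Protocol 7.1.2), with a lower and longer nadir than the 5-day regimen (Protocol 8.2). Events tied to myelosuppression may cluster early, and a percentage-ever is then distorted less.

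Third, the crude AE percentage is not the only safety measure. Mortality at 30 and 60 days, deaths by cause in all randomized subjects, and cycles received are all reported, so a reader can see unequal exposure.

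All three replies limit the size of the problem. None supplies an AE comparison that accounts for time at risk.

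**Conclusion.** The point holds as a gap in the planned safety analysis: the only AE comparison planned is a crude percentage whose window depends on treatment duration, and planned duration is set differently in the two arms. Equal constant rates can then show as a false difference. At 0.2 events per month and 6 guadecitabine cycles, it is about 25 points if TC receives 2 cycles, about 12 if 4, and 0 to 5 if 6. These figures assume a constant rate and windows cut only at death or the end of planned cycles. They shrink with early clustering, or if guadecitabine is stopped early for progression or toxicity.

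A reader might go further and infer that the percentages will point the wrong way, or that guadecitabine will look worse. The documents give neither TC cycles received nor AE rates for either arm of this trial, so neither the direction nor the size can be asserted.

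**What to change.** Keep the crude tables. In SAP 7.4.2, for any Grade 3 or higher AE, any SAE, any fatal AE, and febrile neutropenia, pneumonia and sepsis, add by arm:

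1. Total and median time at risk in the treatment-emergent window.
2. Incidence within 30 days of C1D1, a period covered for nearly all treated subjects.
3. Cumulative incidence of first event to Day 60 and beyond, censored at the end of each subject's window, with death as a competing event. A simple 60-day percentage will not do. Under Protocol 10.2, AE recording generally stops 30 days after the last dose or at new anti-AML therapy, so a subject given one 5-day course is covered for only about 34 days.
4. Exposure-adjusted first-event rates with confidence intervals, split by period (for example Days 1–30, 31–60 and beyond 60), so that early clustering does not distort them.

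The cost is a few tables built from AE, dosing and subsequent-therapy dates already collected, and SAP 6.0 describes the final database lock as still to come. The drawback is that censoring when treatment stops may be informative. The report should say so.
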